5.4.7 Exploratory Analysis

These statistical analyses will be exploratory. Exploratory analyses will be performed on the exploratory analysis set. A separate analysis report for such assessments will be written.

We will compare RECIST and irRECIST criteria for evaluation of the clinical response.

The objective of the statistical analyses of biomarkers is the identification of those markers or combinations of markers which show best association with positive clinical outcome of the study treatment. We will measure the clinical efficacy of that analysis in terms of ORR, CBR, PFS and irPFS.

The exploratory endpoints are PFS, CBR, and ORR based on irRECIST and predictive biomarkers (such as but not limited to PD-1, PD-L1, HIV status). The objective of the exploratory analyses of irRECIST is the characterization of INCMGA00012 clinical activity. The exploratory analysis will be performed only if an adequate number of samples is available at the EoS. Markers (such as but not limited to PD1, PD-L1, HIV, and HPV status) will be evaluated on a univariate level regarding their potential for prediction of the clinical endpoints (ORR, CBR, PFS and irPFS).

Biomarker and response correlations with clinical covariates will be investigated. It will be checked whether covariates can improve the prediction and whether there is an interaction with the biomarkers. Further multivariate techniques (e.g., Multiple Logistic Regression, Cox regression and penalized regressions models) will be deliberated to study combinations of markers. Techniques to control false discovery rate and overfitting (cross-validation) may be considered. Analysis will be performed on exploratory analysis set.

5.5 Safety

All safety tables will list or summarize subjects on the safety set.

These safety assessments will be subjected to clinical review and summarized by appropriate descriptive statistics.

These data will include report of AEs, laboratory analysis, vital signs, ECOG PS, changes in ECG, time of trial dosing, and proportion of interruptions. Terms and severity of AE will be obtained and reported according to the NCI-CTCAE v.5. Statistical summaries of characteristics, frequency, grading, duration, and relationship with treatment will be presented.

5.5.1 Duration and Extent of Exposure of Study Treatment

The study treatment period is defined as the time between the study entry and the last dose of study therapy (INCMGA00012).

Duration and extent of exposure will be based on the safety set.

The following parameters will be calculated:

- b: "Actual Cycle Duration" is the difference between start and stop date dose.
- c: "Actual Cycle Dose Days" is the number of days with dose administration in the cycle, considering the interruptions.
- d: "Actual Total Dose" is the total dose a patient took in a cycle, considering interruptions and reductions.
- e: "Intended Daily Dose per Cycle".
- f: "Intended Cycle Duration".
- g: "Intended Cycle Dose Days".
- A: "Total number of cycles" = 1
- B: "Treatment Duration" = Sum over all cycles of (b).
- C: "Days on drug" = Sum over all cycles of (c).
- D: "Total Actual Total Dose" = Sum over all cycles of (d).

- E: "Mean Intended Daily Dose" = Mean over all cycles of (e).
- F: "Total Intended Duration" = Sum over all cycles of (f).
- G: "Total Intended Dose Days" = Sum over all cycles of (g).
- H: "Intended Total Dose" = G*E
- I: "Actual Average Daily Dose on Dose Days" = D/C
- J: "Ratio for Dose Interruption" = C/G
- K: "Ratio for Cycle Duration" = F/B
- L: "Actual Average Daily Dose Intensity" = I*J*K
- M: "Relative Dose Intensity (RDI)" = L/E*100

The treatment duration (months), number of cycles, days on Drug and Treatment compliance (%) will be summarized in terms of the number of observations, mean, standard deviation (STD), median, minimum and maximum.

Extent of exposure measured as RDI (dose level) will be described with median, interquartile range (IQR) and range. The RDI will be dichotomized in different cutoffs ($\geq 50\%$, $\geq 70\%$, $\geq 80\%$, $\geq 90\%$, $\geq 100\%$) and described with frequencies and percentages.

5.5.2 Dose Delays, Reductions and Discontinuations

The following summaries will be provided:

- Subjects with at least one dose delay.
- Subjects with at least one dose delay due to adverse event.
- Subjects with at least one dose reduction.
- Subjects with at least one dose reduction due to adverse event.
- Subjects with permanently dose discontinuation.
- Subjects with permanently dose discontinuation due to adverse event.

5.5.3 Concomitant Medications

The number and percent of unique patients taking concomitant medications will be summarized by therapeutic classification, coded term, and dose level. Elective surgeries/procedures performed during the study will be presented in a listing.

The following are conventions that will be used to classify individual medications as prior and/or concomitant:

- Medications with stop dates prior to screening visit date will be considered prior.
- Medications with missing stop dates or stop dates the day of or after screening visit date will be considered concomitant, regardless of start date. Additionally, if the start date is prior to screening visit date or missing, the medication will also be considered prior.

Frequencies and by-subject listing of all prior and concomitant medications will be provided, containing variables listed on Prior/Concomitant Assessment eCRF, their corresponding categories (Prior or Concomitant), and WHO Anatomical Therapeutic Chemical (ATC) level 2 and ATC Name.

5.5.4 Adverse Events

All AEs will be recorded on the eCRF "Adverse Events" page and will be coded using the current version of MedDRA® to give a system organ class (SOC) and preferred term (PT) for each event. All adverse event safety data will be updated to the version of MedDRA that is current at the time of the database lock and statistical analyses. Adverse events will be coded with grades defined according to CTCAE V5.0 criteria.

Treatment-emergent AEs (i.e., those events occur after the first study medication administration and were not present at baseline or worsened in severity following the start of treatment) will be tabulated. The TEAE will be tabulated according to intensity and causality. If intensity of an AE or causality of an AE to the study medication is missing, a worst-case scenario will prevail (severe in intensity or probably related will be assumed). In the summary tables the number of subjects with events and the number of events will be presented.

The onset date of an AE will be compared to the date of first dose of study drug to determine whether the AE is treatment emergent. Adverse events with an onset date on or after the date of first dose of study drug will be classified as treatment emergent.

All deaths and SAEs, regardless of cause, from treatment start until 28 days after final dose of treatment. Non-fatal AEs occurring after treatment start regardless of cause, up until 28 days after final dose of treatment or until start of new anti-cancer treatment, whichever is first. Disease progression is not considered a treatment emergent adverse event unless the patient dies of disease prior to 28 days after discontinuation of treatment. Events that are continuations of baseline abnormalities are considered treatment emergent adverse events only if there is an increase in grade over baseline, or if there is an increase following a decrease during the study.

Treatment emergent adverse events with cause possibly, probably or definitely related to treatment as judged by the investigator. Events that are continuation of baseline abnormalities are not considered treatment related unless there is an increase in grade, or if there is an increase following a decrease, and the increase is judged by the investigator to be due to treatment.

Descriptive statistics will be used to characterize the profiles of treatment-related AEs, treatment-related deaths, SAEs, treatment-related delays, dose reductions, and/or treatment discontinuations. All AEs will be graded according to the current version of the NCI-CTCAE v.5 and the Medical Dictionary for Regulatory Activities (MedDRA).

The following summaries will be provided:

- Summary of Adverse Events
 - o Subjects with at least one Adverse Event (AE)
 - o Subjects with at least one Treatment Emergent AE (TEAE)
 - o Subjects with at least one related study drug TEAE
 - o Subjects with at least one grade 3 or 4 or 5 TEAE
 - o Subjects with at least one related grade 3 or 4 or 5 TEAE
 - o Subjects with at least one serious TEAE
 - o Subjects with at least one related serious TEAE
 - o Subjects with at least one non-serious TEAE
 - o Subjects with at least one Adverse Event of Special Interest (AESI)
 - o Deaths due to TEAE
 - o Subjects with TEAE leading to Discontinuation of Study Treatment
 - o Subjects dropped out due to AE.
- Summary by SOC and PT of the number and percentage of subjects reporting each:
 - o Treatment Emergent Adverse Events
 - o Treatment Emergent Adverse Events by Treatment and Hematologic
 - o Treatment Emergent Adverse Event Related to Study Drug
 - o Related Treatment Emergent Adverse Event by Treatment and Hematologic
 - o AESI Treatment Emergent Adverse Events
 - o Treatment Emergent Adverse Events with Grade 3 or 4 or 5

- Related Treatment-Emergent Adverse Event with Grade 3 or 4 or 5
- Serious Treatment Emergent Adverse Event
- Serious and Related Treatment Emergent Adverse Event
- Treatment Emergent Adverse Event by Maximum Severity
- Treatment Emergent Adverse Event Leading to Discontinuation of Study Drug

5.5.5 Clinical Laboratory Parameters

The following summaries will be produced for all hematology and biochemistry laboratory parameters:

- Shift tables of low, normal, high distribution (n; %) with respect normal ranges of center, at each post-baseline cycle by baseline (cycle 1 day 1) distribution.
- Shift tables of low, normal, high distribution (n; %) of clinically significant at each post-baseline cycle comparing with baseline (cycle 1 day 1) distribution.
- The value distribution will be displayed using a serial box plot at each cycle.

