3 STUDY DESIGN

3.1 Description of Study Design

This is a multicenter, open-label, single-arm, phase II clinical trial to evaluate the efficacy and safety of the INCMGA00012 (retifanlimab) in progressive advanced PSqCC patients, previously treated or not with chemotherapy.

The study population consists of male patients age ≥ 18 years with advanced PSqCC that are presenting with progressive disease. Patients that have received prior treatment of locally recurrent and/or metastatic disease with platinum-based chemotherapy regimens are not excluded.

In the absence of progression of disease or unacceptable toxicity, treatment with INCMGA00012 (retifanlimab) will continue based on physician's criteria for up to 2 years.

Tumor assessments per RECIST v.1.1 and irRECIST will be performed approximately every eight weeks (± 7 days) for the first 6 months and every 12 weeks (± 7 days) thereafter until PD, treatment discontinuation, the start of new anti-cancer treatment, withdrawal of consent, death, or the end of study (EoS), whichever occurs first. Tumor assessments will be performed on the specified schedule regardless of treatment delays.

For estimation of ORR, CBR, DoR, and PFS tumor response will be based on RECIST v.1.1. In patients who continue treatment beyond radiographic PD per RECIST v.1.1, tumor response (ORR, CBR, and PFS) may continue to be assessed using irRECIST criteria until study treatment discontinuation.

Safety assessments will include the incidence, nature, and severity of AEs and laboratory abnormalities graded per the NCI-CTCAE v.5.0. Laboratory safety assessments will include the regular monitoring of hematology, blood chemistry, coagulation, and thyroid function testing. A schedule of assessments is provided in **Appendix 1**.

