7.1 AEs Definitions

An AE is any untoward medical occurrence in a patient or clinical investigation subject administered a pharmaceutical product and which does not necessarily have to have a causal relationship with this treatment. An AE can therefore be any unfavorable and/or unintended sign (including an abnormal laboratory finding), symptom, or disease temporally associated with the use of an IMP, regardless of whether it is considered related to the IMP or not.

An abnormal test finding should only be reported as an AE if meets any of the following criteria:

- Is associated with accompanying symptoms and a general diagnostic term, including the symptoms and the abnormal test finding, cannot be defined.
- Requires additional diagnostic testing or medical/surgical intervention, leads to a change in study drug(s) dosing or discontinuation from the study.
- Needs additional concomitant drug treatment.
- Is considered to be an AE by the investigator or by the Sponsor.

Diagnostic and therapeutic non-invasive and invasive procedures, such as surgery, should not be reported as AEs. However, the medical condition for which the procedure was performed should be reported if it meets the definition of an AE. For example, an acute appendicitis that begins during the AE reporting period should be reported as the AE and the resulting appendectomy should be recorded as treatment of the AE.

The causal relationship between an AE and the IMP will be defined as follows:

Unrelated: The temporal association between the AE and the administration of the IMP makes a causal relationship unlikely, or the subject/patient's clinical state or the study procedure/conditions provide a sufficient explanation for the AE.

Related: The temporal association between the AE and the administration of the IMP makes a causal relationship possible, and the subject/patient's clinical state or the study procedure/conditions do not provide a sufficient explanation for the AE.

Each AE must be assessed by the Investigator as to whether or not there is a reasonable possibility of causal relationship to the IMP.

The descriptions and grading scales found in the revised NCI-CTCAE v.5.0 criteria will be utilized for all toxicity reporting. A copy of the NCI-CTCAE v.5.0 criteria can be downloaded from the CTEP website:

(https://ctep.cancer.gov/protocolDevelopment/electronic_applications/docs/CTCAE_v5_Quick_Reference_8.5x11.pdf).

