5 STATISTICAL METHODS

5.1 General Methodology

The statistical analysis will be conducted following the principles as specified in International Conference on Harmonization (ICH) Topic E9 (CPMP/ICH/363/96). The significance level will be $\alpha=0.05$ for all tests. As an exploratory study, multiple testing without adjustment of the significance level is considered acceptable.

Definition of baseline: For each safety or efficacy parameter, the last valid assessment made before first study drug administration will be used as the baseline for all analyses of that safety or efficacy parameter unless otherwise specified.

Continuous data will be summarized in terms of the number of observations, mean, standard deviation (SD), median, minimum, maximum, and first and third quartiles, unless otherwise stated. Where data are collected over time, both the observed data and change from baseline will be summarized at each time point.

The minimum and maximum will be reported to the same number of decimal places as the raw data recorded in the database. The mean, median, and first and third quartiles will be reported to one more decimal place than the raw data recorded in the database. The SD will be reported to two more decimal places than the raw data recorded in the database. In general, the maximum number of decimal places reported shall be four for any summary statistic.

Categorical data will be summarized in terms of the number of subjects providing data at the relevant time point (n), frequency counts and percentages. Changes from baseline in categorical data will be summarized using shift tables where appropriate.

Percentages will be presented to one decimal place. A percentage of 100% will be reported as 100%. Percentages will not be presented for zero counts. Unless otherwise stated, percentages will be calculated using n as the denominator, for frequency tables not assessed by time point the set will be used as denominator. If sample sizes are small, the data displays will show the percentages, but any textual report (e.g., clinical study report) will describe frequencies only.

P-values greater than or equal to 0.001, in general, will be presented to three decimal places. However, if a P-value is only presented to four decimal places (by SAS) it will not be rounded again but will be presented to four decimal places. P-values less than 0.0001 will be presented as "<0.0001".

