5.5.7 Physical Examination

The following summaries will be produced for all physical examination's parameters:

- Shift tables of low, normal, high distribution (n; %) at each post-baseline cycle by baseline (cycle 1 day 1) distribution.

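### SAP 5.5.5 plans no CTCAE-graded laboratory summary, although both documents say laboratory abnormalities are graded, and its normal-range shift table cannot separate degrees of abnormality

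*SAP*

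**What the plan says.** Protocol 3.1 makes the commitment, and SAP 1.4 repeats it: "Safety assessments will include the incidence, nature, and severity of AEs and laboratory abnormalities graded per the NCI-CTCAE v.5.0".

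SAP 5.5.5 lists three outputs for haematology and biochemistry:

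- "Shift tables of low, normal, high distribution (n; %) with respect normal ranges of center, at each post-baseline cycle", compared with cycle 1 day 1.
- "Shift tables of low, normal, high distribution (n; %) of clinically significant at each post-baseline cycle", again compared with cycle 1 day 1. The section does not define clinical significance.
- "The value distribution will be displayed using a serial box plot at each cycle".

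SAP 5.1 adds a general rule for continuous data: "Where data are collected over time, both the observed data and change from baseline will be summarized at each time point". The safety endpoint itself (Protocol 2.2.1, SAP 3.3) is worded as change from baseline in targeted laboratory results.

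CTCAE grade appears in the outputs only for adverse events (SAP 5.5.4). Entry to those tables is conditional under Protocol 7.1: "An abnormal test finding should only be reported as an AE if meets any of the following criteria". The criteria include accompanying symptoms, further testing or intervention, a change in dosing or discontinuation, added drug treatment, and investigator or sponsor judgement.

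For physical examination, SAP 5.5.7 uses the same template: "Shift tables of low, normal, high distribution (n; %) at each post-baseline cycle by baseline (cycle 1 day 1) distribution".

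SAP 5.7, which lists changes from the protocol, does not mention laboratory grading.

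**The concern.** The documents promise graded laboratory abnormalities, and the section that specifies the laboratory outputs does not deliver them. Grade matters in this trial because Protocol Table 1 acts on it. For hepatic events, for example, the action changes between grade 2 and grade 3. A reader of the study report will want to know how many patients had a worst value of grade 3 or 4 for each parameter, and no laboratory table answers that.

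Two smaller points belong to the same section of the SAP:

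- SAP 5.5.5 names only haematology and biochemistry. Protocol 3.1, Protocol 6.5.1 and Appendix 1 list thyroid function separately, and Appendix 1 schedules it at every cycle. SAP 5.5 names no thyroid summary, although hypothyroidism is the most frequent event in Protocol Table 4 (47 of 578, 8.1%).
- A physical examination by body system (Protocol 6.5.3) has no low or high.

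**Working it through.** The plan gives no figure of its own on this point, so the check applies its classification rule and then follows each output that could make up for it.

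**1. Normal-range shift table.** Inputs: high means above 1 x ULN (SAP 5.5.5, centre's range). Eligible AST/ALT is at most 2.5 x ULN, or at most 5 x ULN with liver metastases (Protocol 4.2, criterion 11). The post-baseline values are illustrative. Ratio = later value / baseline value, both in multiples of ULN.

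| Baseline | Later | Ratio | Shift shown |
|---|---|---|---|
| 0.8 | 3 | 3.75 | normal to high |
| 0.8 | 20 | 25 | normal to high |
| 1.5 | 10 | 6.7 | high to high |
| 2.5 | 10 | 4 | high to high |
| 4 (liver metastases only) | 10 | 2.5 | high to high |
| 5 (liver metastases only) | 20 | 4 | high to high |

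From a normal baseline, a 3.75-fold and a 25-fold rise share one cell. From any baseline above ULN no upward shift is possible, although a downward one is. The documents give no CTCAE cut-offs in multiples of ULN, so no grades are assigned to these values here.

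**2. Other laboratory outputs.** Take 4 to 10 x ULN. The change from baseline is 10 - 4 = +6 x ULN, which enters the SAP 5.1 summary and moves the box plot. The patient may also move in the clinically significant table, if the baseline was judged not significant and the later value significant. These outputs register the rise, but they describe distributions or an undefined judgement. None gives n (%) by worst grade.

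**3. The AE route.** Protocol 5.3 requires ALT, AST and bilirubin below grade 2 before re-treatment, and Table 1 attaches withholding or discontinuation to higher hepatic grades. A resulting dosing change meets a Protocol 7.1 criterion, so the event becomes an AE, is graded, and appears by maximum severity and among grade 3-5 events (SAP 5.5.4). However, the Protocol 5.3 re-treatment list also says that transient asymptomatic laboratory elevations up to grade 3 need no interruption if they are clinically insignificant and have been discussed with the medical monitor. Without symptoms, further work-up or treatment, such a value enters the AE tables only by investigator or sponsor judgement.

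**4. Timing.** The SAP 5.5.5 tables are set out by cycle. Protocol 5.3 calls for re-evaluation at least weekly when re-treatment criteria are not met, and Appendix 1 schedules haematology and chemistry at End of Treatment. Neither is a cycle visit, so values around a delay or a stop may fall outside the tables.

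**5. Scale.** One patient in 18 is 1/18 = 5.6%.

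**The case against.** The strongest reply is that little is hidden. The endpoint is change from baseline, which SAP 5.1 delivers. The grading sentence in Protocol 3.1 and SAP 1.4 does not promise a particular table. Hepatic abnormalities that trigger withholding or discontinuation become graded AEs. SAP 5.5 mentions summaries of grading, and SAP 6.2 leaves the full list of outputs to a separate document that could include a graded table. The safety analysis is descriptive and no decision rule depends on it.

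Much of this stands, and it rules out some stronger readings:

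- A reader might infer that a rise from 4 to 10 x ULN would show as no change anywhere in the plan. That is true only of the normal-range shift table, and a baseline of 4 x ULN is eligible only with liver metastases.
- A reader might infer that no planned output can show patients crossing the grades in Table 1. Crossings that change dosing reach the graded AE tables.
- A reader might infer that patients who stop for toxicity drop out of the laboratory tables. Their values up to stopping remain in the tables for their cycles. What may be missed are unscheduled and End of Treatment values.

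Two parts of the reply do not carry. The SAP 5.5 sentence on grading sits with the reporting of AE terms and severity and does not specify a graded laboratory table. An output list that can be updated without changing the SAP does not alter the method that SAP 5.5.5 states.

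**Conclusion.** The point holds in limited form. SAP 5.5.5 does not deliver the graded laboratory summary that both documents lead the reader to expect, and its normal-range table puts every value above ULN into one category. The uncovered part is abnormalities that trigger no action and so need not become AEs, together with values taken outside cycle visits.

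The number of affected patients cannot be derived from the documents. The 5.6% is only what one uncounted patient would represent among 18, not an estimate that one will be missed. The conclusion assumes that the outputs follow SAP 5.5.5 and 5.1 as written and that laboratory findings are reported as AEs under the Protocol 7.1 criteria. The primary analysis and the sample size are unaffected. The change is worth making because it is cheap and gives a more informative table.

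**What to change.** In SAP 5.5.5, add for each gradable parameter a shift table from baseline CTCAE v.5.0 grade to worst on-treatment grade. Include unscheduled and End of Treatment values, and give n (%) of patients reaching grade 3-4. Define baseline here as in SAP 5.1 (last valid value before first dose), because the cycle 1 day 1 panel may be omitted when screening bloods fall within 72 hours of the start of treatment.

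Add TSH, free T3 and free T4 as baseline to worst low/normal/high category.

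In SAP 5.5.7, replace low/normal/high by normal/abnormal.

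The cost is a few more output tables from data already collected. No visit, procedure or sample size changes.
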